At the screening visit, a targeted physical examination, if indicated based on subject's complete medical history, may be performed by a study clinician licensed to make medical diagnoses and listed on the Form FDA 1572 as the site principal investigator or sub-investigator. For pregnant women, information from a physical exam performed by the subject's clinician may also be used. On Day 1, prior to the vaccination, and as needed at follow-up visits after vaccination, a targeted physical examination may be performed by a study clinician licensed to make medical diagnoses and listed on the Form FDA 1572 as the site principal investigator or sub-investigator, if indicated based on the subject's interim medical history. Targeted physical examinations are performed to investigate further symptoms reported by the subject that may have relevance to the study.

Vital signs (oral temperature, pulse, and blood pressure) will be collected on Day 1 prior to the administration of the study treatment and on subsequent visits as denoted in the study schedule.

Vital signs assessed on Day 1 prior to study vaccination will be considered as baseline. Subjects will be asked to not eat or drink anything hot or cold, or smoke within the 10 minutes prior to taking an oral temperature.

Solicited event assessments will include an assessment of solicited adverse events occurring from the time of vaccination (Day 1) through Day 8. These assessments include injection site (local) reactions of ecchymosis (bruising), erythema (redness), induration (hardness)/edema (swelling), pain, and tenderness as well as systemic reactions including fever, feverishness (chills/shivering/sweating), fatigue (tiredness), malaise (general unwell feeling), myalgia (body aches/muscular pain exclusive of the injection site), arthralgia (joint pain exclusive of the injection site), headache, nausea, and allergic reaction (pruritus/urticaria). Pre-administration solicited systemic event assessments will be performed prior to study vaccination to establish baseline, then the study vaccination will be given.

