9.2. Methods and Timing for Assessing, Recording, and Analyzing Safety Parameters

9.2.1. Adverse Events

Adverse Event:

ICH E6 defines an AE as any untoward medical occurrence in a patient or clinical investigation subject administered a pharmaceutical product regardless of its causal relationship to the study treatment. FDA defines an AE as any untoward medical occurrence associated with the use of a drug in humans, whether or not considered drug related.

An AE can therefore be any unfavorable and unintended sign (including an abnormal laboratory finding), symptom, or disease temporally associated with the use of medicinal (investigational) product. The occurrence of an AE may come to the attention of study personnel during study visits and interviews of a study recipient presenting for medical care, or upon review by a study monitor.

AEs, including solicited local (injection site) and systemic (subjective and quantitative) reactions, will be captured on the appropriate data collection form and eCRF. Information to be collected for unsolicited non-serious AEs includes event description, date of onset, assessment of severity, relationship to study product and alternate etiology (assessed only by those with the training and authority to make a diagnosis and listed on the Form FDA 1572 as an investigator), date of resolution, seriousness and outcome. FWs will be trained on the assessment of local and systemic reactogenicity. If the subject reports an AE that is either not included among the solicited AEs or is a grade 3 solicited AE, then the FW will contact a study clinician. The study

clinician will either visit the participant at home or the participant will be referred to the study health center based on the FW's assessment. AEs occurring during the trial collection and reporting period will be documented appropriately regardless of relationship. AEs will be followed through resolution.

Any medical condition that is present at the time that the subject is screened will be considered as baseline and not reported as an AE. However, if the severity of any pre-existing medical condition increases, it should be recorded as an AE.

All AEs must be graded for severity and relationship to study product (see definitions). Adverse events characterized as intermittent require documentation of onset and duration of each episode. The start and stop date of each reported AE will be recorded on the appropriate data collection form and eCRF.

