11.4.2. Safety Data

Maternal safety and tolerability, and fetal/infant outcomes will be summarized for the Safety Analysis Population.

Solicited AEs will be summarized by severity on days 4 and 8 after the study vaccination and as the maximum severity over the 8 days. Additionally, solicited AEs will be analyzed by taking the most severe response over the follow-up period, dichotomizing into a binary variable (none versus mild, moderate, or severe) and using standard techniques, such as exact confidence intervals, to summarize the proportion of subjects reporting each symptom, any injection site symptom, and any systemic symptom.

Unsolicited AEs will be coded by Medical Dictionary for Regulatory Activities (MedDRA®) for preferred term and system organ class (SOC). The number of SAEs is expected to be small in this trial, so these events will be reported by detailed listings showing the event description, MedDRA® preferred term and SOC, date of study vaccination, event date, severity, relatedness, and outcome for each event. Non-serious unsolicited AEs will be summarized as number and percentage of subjects reporting at least one event in each MedDRA® preferred term and SOC, tabulated by severity and relationship to study product. Additionally, the proportion of subjects and exact 95% confidence intervals of AEs in aggregate and by MedDRA® categories will be computed.

The proportion of subjects reporting solicited or unsolicited AEs may be compared between treatment arms using Fisher's exact test. The number of untoward fetal outcomes, perinatal complications, and major congenital abnormalities is expected to be small and so these events will be reported by a detailed listing including the event description, MedDRA® preferred term and SOC, relevant dates (study vaccination and AEs), severity, relatedness, and outcome for each event. If more than 5% of pregnant women experience untoward fetal outcomes, perinatal complications, or infants born with major congenital abnormalities, the proportion of subjects with such events will be compared between the BOOSTRIX and Td treatment arms using Fisher's Exact test.

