### 9.3.1. Solicited Events and Symptoms

Systemic solicited adverse events will be collected in maternal subjects pre-vaccination, and systemic and local solicited adverse events will be collected 30 minutes post-vaccination and then daily for 7 days after vaccination and graded on a scale of 0 (absent), 1 (mild), 2 (moderate) and 3 (severe). Systemic events include fatigue, headache, nausea, allergic reaction, myalgia, malaise, arthralgia, feverishness and fever. Local events include pain at injection site, tenderness, ecchymosis, erythema, induration, and measurements of ecchymosis, erythema, and induration ([Table 8](#)).

The proportion of subjects reporting at least one solicited adverse event will be summarized for each solicited adverse event, any systemic symptom, any local symptom, and any symptoms. The 95% CI calculated using Clopper-Pearson methodology from a binomial distribution (SAS Proc Freq with a binomial (exact) option) will be presented and a Fisher's exact test will be performed to test for the difference in the proportion of subjects reporting a solicited adverse event ([Table 49](#) and [Table 50](#)).

For each systemic and local event, any systemic event, any local event, and any solicited event, the maximum severity over 7 days after vaccination will be summarized for the Safety population. The number and percentage of subjects reporting each event will be summarized by the maximum severity and treatment group ([Table 51](#)).

The number of subjects reporting a solicited adverse event will be summarized for each day post vaccination by treatment group in a summary table ([Table 52](#), [Table 53](#), and [Table 54](#)) and graphically in a bar chart ([Figure 225](#) and [Figure 226](#)).

Solicited adverse events by subject will be presented in [Listing 10](#) and [Listing 11](#).

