	Not Reported																		
Ecchymosis	None																		
	Mild																		
	Moderate																		
	Severe																		
	Not Reported																		
Erythema	None																		
	Mild																		
	Moderate																		
	Severe																		

Table 52: Number and Percentage of Maternal Subjects Experiencing Solicited Events by Symptom, Severity, Day Post Dosing, and Treatment Group – BOOSTRIX (continued)

BOOSTRIX (N=X)																			
Symptom	Severity	Pre-Dose		Post-Dose		Day 2		Day 3		Day 4		Day 5		Day 6		Day 7		Day 8	
		n	%	n	%	n	%	n	%	n	%	n	%	n	%	n	%	n	%
	Not Reported																		
Induration	None																		
	Mild																		
	Moderate																		
	Severe																		
	Not Reported																		
Ecchymosis Measurement (mm)	None																		
	Mild																		
	Moderate																		
	Severe																		
	Not Reported																		
Erythema Measurement (mm)	None																		
	Mild																		
	Moderate																		
	Severe																		
	Not Reported																		
Induration Measurement (mm)	None																		
	Mild																		
	Moderate																		
	Severe																		
	Not Reported																		
Note: N = Number of subjects in the Maternal Safety Population randomized to receive intrapartum BOOSTRIX. Severity is the maximum severity reported post dosing for each subject for each day.																			

Tables with Similar Format:

**Table 53: Number and Percentage of Maternal Subjects Experiencing Solicited Events by Symptom, Severity, Day Post Dosing, and Treatment Group – Td**

**Table 54: Number and Percentage of Subjects Experiencing Solicited Events by Symptom, Severity, Day Post Dosing, and Treatment Group – All Subjects**

**14.3.1.2 Unsolicited Adverse Events****Table 55: Summary of Unsolicited Adverse Events by MedDRA System Organ Class and Preferred Term, and Treatment Group – BOOSTRIX – Maternal Subjects**

MedDRA System Organ Class	MedDRA Preferred Term	Day 1-8 Post Dose (N=X)				Days > 8 Post Dose (N=X)				Any Time (N=X)			
		n	%	95% CI	Events	n	%	95% CI	Events	n	%	95% CI	Events
Any SOC	Any PT	x	xx	xx, xx	x	x	xx	xx, xx	x	x	xx	xx, xx	x
[SOC 1]	Any PT												
	[PT 1]												
	[PT 2]												
[SOC 2]	Any PT												
	[PT 1]												
	[PT 2]												

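### As written, the solicited-event rule would count systemic symptoms that were already present at the same grade before vaccination and merely persist

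*Protocol*

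**What the plan says.** A baseline is collected. Protocol 8.1 states: "Pre-administration solicited systemic event assessments will be performed prior to study vaccination to establish baseline". SAP 9.3.1 confirms it: "Systemic solicited adverse events will be collected in maternal subjects pre-vaccination".

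The analysis rule does not mention that baseline. Protocol 11.4.2 works by "taking the most severe response over the follow-up period, dichotomizing into a binary variable (none versus mild, moderate, or severe". SAP 9.3.1 says: "The proportion of subjects reporting at least one solicited adverse event will be summarized for each solicited adverse event" (Tables 49 and 50, with a Fisher's exact test between arms), and for Table 51 "the maximum severity over 7 days after vaccination will be summarized for the Safety population".

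The pre-dose grade appears in the by-day displays (Tables 52-54, Figures 225-226) as one more time point. The note to Table 52 describes grades as reported, not relative to the woman's own baseline: "Severity is the maximum severity reported post dosing for each subject for each day".

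Protocol 9.2.1, a section that expressly covers solicited reactions, has a baseline principle: "Any medical condition that is present at the time that the subject is screened will be considered as baseline and not reported as an AE". It adds that "if the severity of any pre-existing medical condition increases, it should be recorded as an AE".

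**The concern.** The solicited symptoms include fatigue, malaise, headache, nausea and myalgia. Pregnant women may have these for reasons unrelated to the injection, and that is a good reason to grade them before the dose. A rule that looks only at the worst post-dose grade cannot separate a new reaction from a complaint that was already there.

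Frequency and severity of solicited events is a primary tolerability outcome (Protocol 3.2.1). The study tests no specific null hypothesis, so the reported rates are themselves a main product. If they include unchanged pre-existing symptoms, they overstate how often the vaccines cause systemic reactions, and the comparison of BOOSTRIX with Td becomes less sensitive.

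**Working it through.** **1. The plan's own safety figure.** Protocol Table 9 (SAP Table 3) gives the chance of at least one event in an arm, 1 − (1 − f)^n for true frequency f. With n = 133 and 67 this gives 1.32/0.67, 12.46/6.48, 73.73/49.00 and 100.0/99.91%, which matches every cell. The counting rule does not affect this table. No power is stated for comparing solicited events between arms.

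**2. The rule applied to one woman.** Pre-dose fatigue Grade 1, Day 4 Grade 1, Day 8 Grade 0. Her maximum post-dose grade is 1, so she falls in the any category of Tables 49-51. Nothing in Protocol 11.4.2 or SAP 9.3.1 takes her out.

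**3. Effect on the rate.** Let p be the share of women whose pre-dose symptom persists at the same grade (an assumption; the documents give no value), and r the risk of a new symptom in the others. The any-grade rate is p + (1 − p)r. Take r = 28%, from the 28.1% fatigue figure in Protocol 2.3.1 (US adults, 14-day follow-up):

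- p = 10%: 0.10 + 0.90 × 0.28 = 35.2%
- p = 20%: 0.20 + 0.80 × 0.28 = 42.4%
- p = 40%: 0.40 + 0.60 × 0.28 = 56.8%

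**4. Effect on the absolute arm difference.** Under the any-grade rule the difference is [p + (1 − p)rT] − [p + (1 − p)rC] = (1 − p)(rT − rC). If unchanged symptoms are dropped and nobody worsens, it is (1 − p)rT − (1 − p)rC, which is the same. A 10-point difference in new-onset risk reads 9, 8 or 6 points at p = 10%, 20% or 40% under both rules. If women symptomatic at baseline worsen with risks wT and wC, the new-or-worsened rule adds p(wT − wC). The full difference returns only if worsening is as likely as new onset in each arm (w = r).

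**5. Effect on risk ratio and power.** Assumed new-onset risks are 30% (BOOSTRIX) and 15% (Td), with 133 and 67 women. The test is a two-sided Fisher test at 0.05; the documents state that level only for the PT t-test, so it is assumed here. Power is exact.

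| p | Any-grade rates | Difference (points) | Risk ratio | Power | Power, new-or-worsened, nobody worsens | Power, new-or-worsened, w = r |
|---|---|---|---|---|---|---|
| 0% | 30.0 v 15.0% | 15.0 | 2.00 | 63% | 63% | 63% |
| 10% | 37.0 v 23.5% | 13.5 | 1.57 | 44% | 56% | 63% |
| 20% | 44.0 v 32.0% | 12.0 | 1.38 | 34% | 48% | 63% |
| 30% | 51.0 v 40.5% | 10.5 | 1.26 | 25% | 42% | 63% |
| 50% | 65.0 v 57.5% | 7.5 | 1.13 | 17% | 27% | 63% |

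Under the new-or-worsened rule the risk ratio is 2.00 in every row. The difference equals the third column if nobody worsens and is 15.0 points if w = r.

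**The case against.** The strongest reply is that the documents nowhere say that unchanged symptoms are counted. Protocol 9.1 defines solicited events as occurring from the time of vaccination, 9.2.2 calls them adverse events, and 9.2.1 removes pre-existing conditions unless they worsen. On that reading Protocol 11.4.2 summarizes events that have already been filtered, and its silence is not a contrary rule. This part stands: the defect is a rule left undefined and inconsistent between sections, not an explicit instruction to count persistent symptoms.

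It does not settle the matter. The 9.2.1 principle refers to a medical condition present at screening, which may be up to 30 days before the dose. It is not tied to the Day 1 symptom grades, and the SAP does not carry it over; SAP 9.3 includes every reported adverse event. Nor does another filter do the work: Listing 10 records alternate etiology for Grade 3 events only, and exclusion criterion 3 allows minor residual symptoms of a nearly resolved illness. Where the protocol wants a baseline in the grading it says so, as for bradycardia in Table 7. The symptom scales contain no such reference.

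Other points stand in part. Participants must be healthy, which may keep p small. The blinded Td arm shows the background rate. The protocol only says that arms may be compared, although the SAP commits to the test. The worst post-dose grade is also a defensible, conservative summary, which is a reason to keep it.

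A reader might infer that the rule dilutes the absolute arm difference and that the fix would restore it. Step 4 shows otherwise: persistent symptoms cancel between randomized arms.

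**Conclusion.** The concern holds as a gap in the definition of a primary tolerability outcome. Taken literally, the analysis text counts unchanged pre-dose systemic symptoms, at odds with the principle in Protocol 9.2.1 and with the purpose of the pre-dose grading. The consequences would be higher systemic rates in both arms, a risk ratio closer to 1 and lower Fisher power. Randomization means that neither arm is favoured. The absolute difference recovers only to the extent that women symptomatic at baseline worsen after vaccination.

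The size is not known. The figures above rest on an assumed p, on complete persistence at the same grade, on reaction rates from US adults followed for 14 days, and on assumed arm risks. It would be wrong to state as fact that the trial's rates are inflated, because the documents give no pre-dose symptom rate. It would also be wrong to say that baseline is ignored altogether: it is displayed by day, but no planned summary pairs it with the woman's own post-dose grade. Local reactions are unaffected; SAP 9.3.1 collects only systemic events before the dose.

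**What to change.** In SAP 9.3.1, add a second version of the systemic rows of Tables 49-51 that counts a woman only if a post-dose grade exceeds her own Day 1 pre-dose grade for that symptom (new or worsened). Derive the Any Systemic Symptom row from the same definition. Derive Any Symptom from it together with the local reactions, which stay as they are. Report this version beside the any-grade version, and state in both documents how the Day 1 grade relates to the baseline principle in Protocol 9.2.1. The change concerns tabulation only, not halting or clinical management.

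The data are already collected, so the cost is one derivation and one extra table version. There is a real downside: the new-or-worsened count misses a symptom that resolves and then recurs at the same grade after the injection. The any-grade version must therefore be kept.

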3.2. Study Outcome Measures

3.2.1. Primary

Safety and Tolerability:

- Safety in pregnant women: Frequency and severity of study vaccine-related serious adverse events (SAEs), and all SAEs in pregnant women from study vaccination through 6 months postpartum, description and comparison between those receiving BOOSTRIX and Td.
- Safety in pregnant women and fetuses/infants: Frequency and severity of adverse events specific to pregnancy, in pregnant women and their infants (as delineated in [Section 9.2.4](#)), description and comparison between those receiving BOOSTRIX and Td.
- Tolerability in pregnant women: Frequency and severity of solicited injection site and systemic reactogenicity events from study vaccination until 7 days following vaccination (Day 8).
- Tolerability in pregnant women: Frequency and severity of all unsolicited non-serious AEs from day of study vaccination to Day 31, description and comparison between those receiving BOOSTRIX and Td.

- Safety in the infants: Frequency and severity of study vaccine-related serious adverse events, and all SAEs in infants from birth through 6 months of age, description and comparison between infants born to women vaccinated with BOOSTRIX and Td.

Immunogenicity:

- Infant humoral immunity: Geometric Mean Concentration (GMC) of serum IgG antibodies to PT as measured by Enzyme-Linked Immunosorbent Assay (ELISA) at birth between infants born to women vaccinated with BOOSTRIX and Td.

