11.2.3. Sample Size

The study is planned to enroll 200 pregnant women (133 BOOSTRIX, 67 Td).

This will be one of the first studies of maternal Tdap vaccination in an African, low resource setting, and where infants received whole cell, rather than acellular pertussis vaccinations. Thus, this study is intended to obtain preliminary estimates of immune response in this setting; it is not designed to test a specific null hypothesis. The tables below describe the power to detect safety events and the precision available for estimating immune response for the planned sample size. [Table 9](#) indicates the probability of observing one or more safety event, such as solicited injection site or systemic symptom, or an unsolicited adverse event of a particular type within a treatment arm.

Table 9: Power (%) to Detect Safety Events

Event Frequency	N = 133	N = 67
≥0.01% Rare	1.3	<1
≥0.1% Uncommon	12.5	6.5
≥1% Common	73.7	49.0
≥10% Very Common	100.0	99.9

In addition to safety, as a co-primary objective, the study will assess serum PT antibody at birth among infants whose mothers received a single dose of BOOSTRIX, and as secondary and exploratory objectives, the study will assess maternal and infant humoral response to all vaccine antigens. Immune response will be measured by ELISA. [Table 10](#) presents the precision (95% CI) available for estimating GMC of ELISA titers against the vaccine component using assumptions for GMC and standard deviation (SD) for maternal and infant response to Tdap from Munoz et al. [13] and infant response post third dose of primary DTwP vaccine series from Ladhani et al. [34]

Table 10: Precision for Estimating GMC of ELISA Antibody Response

GMC	SD (log-scale)	95% CI Estimate		
		N = 133	N=67	
Maternal ELISA Antibodies at Delivery following maternal Tdap				
PT	51	0.90	43.7	59.5
FHA	184.8	0.73	163.1	209.3
PRN	184.5	1.45	143.8	236.7
FIM	1485.7	1.17	1214.8	1817.0
Infant ELISA Antibodies at Birth following maternal Tdap				
PT	68.8	0.78	60.2	78.7
FHA	234.2	0.67	208.7	262.8
PRN	219	1.38	172.9	277.4
FIM	1867	1.22	1514.7	2301.3
Infant Response post 3rd Dose DTwP following maternal Tdap				
PT	28.8	0.68	25.6	32.3
FHA	25.5	0.60	23.0	28.3
FIM	113.9	0.81	99.1	130.9
Infant Response post 3rd Dose DTwP (no maternal vaccination)				
PT	43.2	0.65	38.6	48.3
FHA	41.1	0.66	36.7	46.1
FIM	224.9	0.97	190.2	265.9
			177.2	285.4

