#### **9.5. Pregnancies**

Every attempt was made to follow subjects to completion of pregnancy to document the outcome, including information regarding any complications with pregnancy and/or delivery. A table summarizing the total pregnancies, number of live births, and number of spontaneous abortions, elective abortions or still births by treatment group will be presented ([Table 75](#)). In addition, a listing of pregnancies and outcomes will be presented ([Listing 18](#), [Listing 19](#), [Listing 20](#), and [Listing 21](#)). A summary of infant size for gestational age at birth by treatment group will be presented in [Table 76](#) and [Figure 233](#).

Pregnancy related adverse events will be collected throughout the study and graded on a scale of 0 (absent), 1 (mild), 2 (moderate) and 3 (severe). Pregnancy related maternal events include pregnancy loss, bleeding during pregnancy or labor, postpartum hemorrhage, postabortal endometritis/salpingitis, preterm rupture of membranes, preterm contractions/labor/delivery, poor fetal growth, hypertension/preeclampsia/eclampsia, chorioamnionitis, postpartum endometritis, gestational diabetes and other pregnancy related AE. Infant events include preterm birth, birth weight, neonatal complications in a term infant, other AE in newborn and congenital abnormality/birth defect ([Table 8](#)).

The proportion of subjects reporting at least one pregnancy related adverse event will be summarized for each pregnancy related adverse event, any maternal symptom, and any infant symptom. The 95% CI will be calculated using Clopper-Pearson methodology from a binomial distribution (SAS Proc Freq with a binomial

(exact) option) will be presented ([Table 77](#) and [Table 78](#)). A Fisher's exact test w the difference in the proportion of subjects reporting a pregnancy related adverse event ([Table 79](#) and [Table 80](#)).

For each pregnancy related event, any maternal event, and any infant event, the maximum severity will be summarized for the maternal and infant Safety populations. The number and percentage of subjects reporting each event will be summarized by the maximum severity and treatment group. ([Table 81](#) and [Table 82](#)). The frequency of pregnancy- and infancy-related adverse events are presented in a bar chart in [Figure 229](#) and [Figure 231](#). The incidence of pregnancy- and infancy-related AEs are presented in [Figure 230](#) and [Figure 232](#).

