Note: N = number of subjects in the Maternal Safety Population randomized to receive intrapartum BOOSTRIX. A subject is only counted once per PT/time point.

Tables with similar format:

**Table 56: Summary of Unsolicited Adverse Events by MedDRA System Organ Class and Preferred Term, and Treatment Group – Td – Maternal Subjects****Table 57: Summary of Unsolicited Adverse Events by MedDRA System Organ Class and Preferred Term, and Treatment Group – All Subjects – Maternal Subjects**

**Table 58: Summary of Unsolicited Adverse Events by MedDRA System Organ Class and Preferred Term, and Treatment Group —Infant Subjects**

MedDRA System Organ Class	MedDRA Preferred Term	BOOSTRIX (N=X)				Td (N=X)				All Subjects (N=X)			
		n	%	95% CI	Events	n	%	95% CI	Events	n	%	95% CI	Events
Any SOC	Any PT	x	xx	xx, xx	x	x	xx	xx, xx	x	x	xx	xx, xx	x
[SOC 1]	Any PT												
	[PT 1]												
	[PT 2]												
[SOC 2]	Any PT												
	[PT 1]												
	[PT 2]												

Note: N = number of subjects in the Infant Safety Population. A subject is only counted once per PT.

**Table 59: Unsolicited Adverse Events by MedDRA System Organ Class and Preferred Term, Maximum Severity, Relationship, and Treatment Group -- Maternal Subjects**

MedDRA System Organ Class	MedDRA Preferred Term	Severity	BOOSTRIX (N=X)						Td (N=X)						All Subjects (N=X)					
			Related		Not Related		Total		Related		Not Related		Total		Related		Not Related		Total	
			n	%	n	%	n	%	n	%	n	%	n	%	n	%	n	%	n	%
Any SOC	Any PT	Any Severity	x	xx	x	xx	x	xx	x	xx	x	xx	x	xx	x	xx	x	xx	x	xx
		Mild																		
		Moderate																		
		Severe																		
SOC 1	Any PT	Any Severity																		
		Mild																		
		Moderate																		
		Severe																		
	PT 1	Any Severity																		
		Mild																		
		Moderate																		
		Severe																		
	PT 2	Any Severity																		
		Mild																		
		Moderate																		
		Severe																		

Note: N = Number of subjects in the Maternal Safety Population.

Note: The difference in the percent of maternal subjects in the BOOSTRIX and Td groups reporting non-serious AEs from day of study vaccination to Day 31 is xx with 95% CI of (xx, xx).

Table with similar format:

**Table 60: Unsolicited Adverse Events by MedDRA System Organ Class and Preferred Term, Maximum Severity, Relationship, and Treatment Group- -- Infant Subjects**

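### Four primary safety outcomes promise a between-arm comparison of frequency and severity, but no planned difference, confidence interval or p-value uses severity grade

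*Protocol*

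**What the plan says.** Protocol 3.2.1 and SAP 3.2.1 list five primary safety outcomes, all worded as frequency and severity. Four add a description and comparison between arms: maternal SAEs, pregnancy-specific events ("Frequency and severity of adverse events specific to pregnancy, in pregnant women and their infants"), unsolicited events ("Frequency and severity of all unsolicited non-serious AEs from day of study vaccination to Day 31, description and comparison") and infant SAEs. The fifth, solicited reactogenicity, has no comparison wording.

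On analysis:

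- **Solicited events.** Protocol 11.4.2 first summarizes them by severity on days 4 and 8 and as the maximum over the period. It then adds an analysis "dichotomizing into a binary variable (none versus mild, moderate, or severe").
- **Between-arm test, Protocol 11.4.2.** "The proportion of subjects reporting solicited or unsolicited AEs may be compared between treatment arms", by Fisher's exact test.
- **Between-arm test, SAP 9.3.1.** The SAP makes this firm for solicited events: a Fisher test "to test for the difference in the proportion of subjects reporting a solicited adverse event" (Table 50).
- **Pregnancy and infant events.** SAP 9.5 and the shells of Tables 79 and 80 give a difference with 95% CI and a Fisher p-value for each event type, any grade versus none.
- **SAEs and unsolicited events.** Notes under Tables 45 and 46 give differences in the percentage with any SAE and any related SAE. The note under Table 59 gives the difference in the percentage of mothers "reporting non-serious AEs from day of study vaccination to Day 31".
- **Severity.** For pregnancy and infant events, "The number and percentage of subjects reporting each event will be summarized by the maximum severity and treatment group" (Tables 81 and 82). Table 51 does the same for solicited events. Tables 59 and 60 break unsolicited events down by grade, and Tables 45 and 46 count Grade 3 unsolicited events by arm.

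**The concern.** If BOOSTRIX made events worse without changing how many women or infants had any event, every planned contrast except the SAE ones would sit near zero. The SAE contrasts would move only so far as the worse events met a seriousness criterion. The severity half of four primary outcomes would then rest on reading two columns side by side.

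The pooling is clinically wide in some rows. Under the grading scale (Protocol Table 8, SAP Table 8), one row of Table 79 combines preterm contractions that settle without treatment with delivery before 37 weeks. The bleeding row combines spotting with bleeding that calls for transfusion. The hypertension row runs from pregnancy-induced hypertension to eclampsia, and the postpartum hemorrhage row from a modest excess loss to transfusion. In Table 80, the neonatal complications row runs from transient signs to more than a week in intensive care.

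**Working it through.** **1. Inputs.** Arm sizes come from Protocol 11.2.3: "The study is planned to enroll 200 pregnant women (133 BOOSTRIX, 67 Td"). As a check on those inputs, the plan's own safety figure (Protocol Table 9, SAP Table 3) is the chance of seeing at least one event, 1 − (1 − p)^N. For p = 0.01%, 0.1%, 1% and 10% this gives:

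- N = 133: 1.32, 12.46, 73.73 and 100.0%
- N = 67: 0.67, 6.48, 49.00 and 99.91%

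The plan prints 1.3, 12.5, 73.7, 100.0 and <1, 6.5, 49.0, 99.9, so its figures reproduce. They concern whether an event is seen within an arm, not a comparison.

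**2. Inventory of the displays.**

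| Events | Between-arm contrast | Severity display |
|---|---|---|
| Solicited | Table 50: any vs none | Table 51, per-arm CI, no contrast |
| Pregnancy | Table 79: any vs none | Table 81, per-arm CI, no contrast |
| Infant | Table 80: any vs none | Table 82, per-arm CI, no contrast |
| Unsolicited, mother | Table 59 note: any vs none | Tables 45 and 59, no contrast |
| SAEs | Tables 45 and 46 notes: SAE vs none | Table 61 listing |

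No cell in the contrast column uses grade. SAE status is seriousness, which is related to grade but is not the same thing.

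**3. Rows affected.** Pregnancy loss and congenital anomaly exist only as Grade 3, so any-versus-none is already severe-versus-none. Preterm rupture of membranes and birth weight have no Grade 1. Any-grade infant preterm birth has the same 37-week threshold as the maternal Grade 3 preterm-delivery category. The other rows of Tables 79 and 80 mix Grade 1 with Grade 3.

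**4. Size.** Power of the two-sided Fisher test is the sum over all (x, y) of Bin(x; 133, p1) × Bin(y; 67, p2) × I[Fisher p ≤ 0.05]. The plan states no level for safety tests, so 0.05 is assumed. The rates are also assumed; the nearest document figure is 61% injection-site pain in BOOSTRIX recipients (Protocol 2.3.1).

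| Contrast | BOOSTRIX vs Td | Rejects |
|---|---|---|
| Any grade | 60% vs 60%, or 40% vs 40% | 4.4% |
| Grade ≥2 | 25% vs 10% | 70.6% |
| Grade ≥2 | 20% vs 10% | 40% |
| Grade 3 | 20% vs 5% | 84.3% |
| Grade 3 | 15% vs 5% | 51.8% |
| Grade 3 | 10% vs 5% | 16% |

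**5. Why side-by-side intervals do not replace a difference.** Take any pain in 81/133 and 41/67: Fisher p = 1.00. Let severe pain be 13/133 = 9.8% (exact 95% CI 5.3 to 16.1) and 1/67 = 1.5% (0.04 to 8.0). The two intervals overlap, and a reader of Table 51 might call the result unclear. The difference is 9.77 − 1.49 = 8.3 points. The Wilson limits are 5.8 to 16.0 and 0.3 to 8.0, so the Newcombe interval is:

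- lower: 8.28 − √[(9.77 − 5.80)² + (7.98 − 1.49)²] = 0.7
- upper: 8.28 + √[(16.01 − 9.77)² + (1.49 − 0.26)²] = 14.6

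This interval excludes zero. No planned table would print it.

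**The case against.** A reader might infer that the plan ignores severity or never lets it be compared. The documents do not support that. Severity appears by arm in Tables 51, 59, 60, 81 and 82, with a confidence interval for each arm and grade in Tables 51, 81 and 82. Figures 225 to 232 also display it. Protocol 11.4.2 introduces the none-versus-any split as an addition to a severity summary.

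A reader might also take the none-versus-any split as a breach of the solicited-event outcome. It is not, because that is the one primary safety outcome with no promised comparison. The mismatch lies in the other four. Table 50 belongs here only because SAP 9.3.1 commits to a between-arm test.

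Other points that stand:

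- Some contrasts are not diluted by mild events (step 3), and the SAE differences capture Grade 3 events that meet a seriousness criterion.
- The power contrast is favorable by construction: any-grade rates exactly equal and large shifts. The source that gives 61% pain gives 1.6% severe pain; a doubling to 3.2% against 1.6% would have about 1% power, and 4.8% against 1.6% about 7%.
- The trial disclaims formal hypothesis testing (Protocol 11.1, SAP 6.8), so power is a secondary yardstick.
- Halting rules (Protocol 9.5) watch for clusters of related Grade 3 events within 7 days of vaccination. They are not a between-arm comparison, but they are a safeguard.

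None of this supplies the estimate. In a trial that estimates rather than tests, a difference with its interval is the natural form of a promised comparison, and the SAP already gives one for every any-grade row.

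**Conclusion.** The point holds as an estimation and reporting gap. Four primary outcomes promise a comparison that includes severity, and no planned between-arm quantity uses grade. A shift from mild to severe could be noticed in the by-arm tables but would not be quantified. The gap matters most for the multi-grade rows of Tables 79 and 80 and for unsolicited events. It does not touch pregnancy loss or congenital anomaly. For the SAE outcomes it matters less, because Protocol 11.4.2 expects few SAEs and lists each with its severity.

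The any-grade test rejects 4.4% of the time when only severity moves. Graded contrasts reach 51.8% to 84.3% for the large shifts assumed and 16% to 40% for doublings. These figures rest on equal any-grade rates, assumed event rates and an assumed 0.05 level, so the benefit is an estimate with a CI more than a powered test.

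**What to change.** In the SAP shells and text:

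- **Tables 79 and 80:** add the BOOSTRIX minus Td difference with 95% CI for Grade 3 in the multi-grade rows and the overall any-event row.
- **Table 59 note:** add the same difference for Grade 2 or higher.
- **Table 50:** for consistency with SAP 9.3.1, add Grade 2 or higher differences for any local, any systemic and each solicited symptom.
- **Protocol 11.4.2:** state that graded differences accompany the none-versus-any summary.

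No extra p-values are needed. If the sponsor prefers not to add these, the alternative is to reword the outcomes so that severity is described and only frequency is compared.

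The cost is wording and some programmed rows from data already in Tables 51, 59, 81 and 82: at most 12 rows in Table 79 (13 less pregnancy loss), 5 in Table 80 (6 less congenital anomaly), 19 in Table 50 (20 less the overall row) and 1 note, 37 in all. The downside is more unadjusted estimates, many on sparse cells with wide intervals. A sentence saying they are descriptive would cover that.
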